Furthermore, a meta-analysis of 5 TMS studies in WC dystonia subjects also demonstrated consistent albeit short-term benefit when TMS was applied at premotor cortex supporting its role in engaging dystonia brain circuitry(38–43) and supporting the idea that these regions are also linked by a common connection. A second potential cortical target is primary sensory cortex. Previous connectivity analysis in WC subjects demonstrated decreased functional connectivity between putamen and primary sensory cortex(27). Among the previous studies applying TMS to WC subjects, the study that showed the longest benefit (2weeks) targeted the primary sensory cortex(44). In this study, TMS stimulation will be applied to the premotor cortex during one visit and to primary sensory cortex during another visit to evaluate the optimal cortical target for modulating putamen activity using TMS in WC subjects.

Design & Procedures

- Describe the study, providing details regarding the study intervention (drug, device, physical procedures, manipulation of the subject or the subject’s environment, etc.). Discuss justifications for placebo control, discontinuation or delay of standard therapies, and washout periods if applicable. Identify procedures, tests and interventions performed exclusively for research purposes or more frequently than standard of care. Include alternative therapies, concurrent therapies discontinued per protocol, risk benefit ratio, and use of tissue/specimens. Discuss monitoring during washout periods if applicable. Include brief description of follow-up, if any.

Consent process and data collection will occur in a private room at the Duke Morreene Road Clinic or Duke brain Imaging Center or Duke Brain Stimulation Center in Red Zone of Duke South. All subjects

will sign an electronic single consent form uploaded to redcap or a printed hard copy. Any subject who wishes to sign their consent forms virtually, a blank consent form will be shared with subjects by redcap or emailed to them prior to the virtual visit. A phone or video visit will then be scheduled. At the virtual visit, an IRB approved study script will be used to review the research study with them for consenting purposes. The subject can then sign the consent form on redcap electronically or mail the signed hard copy to the study staff. The signed consent form will then be scanned and uploaded to Oncore and maestro care. Subjects can opt in or out of visits 2, and 3-5 of the research study.

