Visit 2: 70 FHD subjects and 70 HV from visit 1 will be recruited to undergo a functional MRI brain at Duke BIAC. To assess patient's baseline, subjects will copy a sentence using their dystonic **left or right hand** in fMRI suite alternated by periods of rest using an MRI compatible digital tablet. Writing task and control motor task will be back-projected onto a screen located at the head of the MRI bed using an LCD projector. Subjects will view the screen via a mirror system located in the head coil. Task onset will be electronically synchronized with the MRI acquisition computer using Cigal computer software. Task administration and collection of writing data will be computer controlled. The scanning session will take about 1.5 hr and include structural MRI, DTI, Swan, resting state fMRI and task-based fMRI.

BOLD images will be acquired using a GE Premier Performance 3T MRI scanner, which is an improved version of GE's FDA-approved Premier system, but with better capabilities for high-resolution imaging. All operational parameters on this improved system will be within FDA guidelines to meet the same minimal risk device criteria and ensure safety of human subjects. As such, an Investigational Device Exemption (IDE) is not necessary. The research conducted under this protocol is not to evaluate the safety and efficacy of this device.

A urine drug screen and pregnancy test prior to visits 3-5.

Visits 3, 4 and 5: 5 healthy volunteers who completed visits 1 and 2 will be recruited to undergo development of TMS stimulation protocol at Duke BSRC. Following protocol development, 20 focal hand dystonia subjects who completed visits 1 and 2 will also be recruited to undergo TMS stimulation at Duke BSRC. All 25 subjects will undergo the procedure as detailed below:

[figure not shown]

Figure 3: Sequence of events for research visits 3, 4, and 5. A) Overview of TMS stimulation, writing assessment and fMRI imaging. B) TMS session will be divided into 4 blocks of writing, each 5 minutes.

1. MRI Brain images from visit 2 will be uploaded to a neuro-navigation system (Brainsight: Rogue Research, Montreal, Canada) at the Brain Stimulation Service Stimulation Service Center

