Writer's cramp behavioral data: Endpoints: Objective handwriting parameters of duration of writing, speed of handwriting, fluency of writing movements, axial pen pressure and interpretability of handwriting will be collected using a digital tablet and a pressure sensitive pen for data analysis. Additionally, an observer blinded to subject group will complete Writer's cramp rating scale(46) and BFM Rating Scale from video recordings of subjects performing each writing task (WT-1, WT-2 and WT-3). At the initial visit, patient's medical history will be collected to evaluate appropriateness of dystonia diagnosis. Patient will also be asked about the symptoms and signs of dystonia on rating scales including Adult dystonia and disability rating scale (ADDSD)(45) Burke Fahn Marsden Rating Scale (BFM) and Pain Scale to compare their baseline symptoms before and after all 4 visits.

Sample Size justification: A review of prior research studies employing TMS in writer's cramp and healthy volunteers measuring handwriting showed statistically significant effect sizes of 15-20% on various measures of writing performance using 6-12 subjects per group(38-40,43). A power analysis of our preliminary writing behavior data from 30 subjects in visit 1 demonstrated sample size of 60 in TMS for effect size of 30% with $\alpha = 0.05$. Assuming that I will be able to achieve similar sensitivity in writing metrics, I propose to study 20 patients in TMS group using writing task and fMRI as outcome measures for analysis (visit 1). Due to the pilot nature of fMRI and TMS stimulation parameters, the minimum number of subjects needed to calculate statistical power were selected. Therefore, in order to reach pilot data set of 20 patients in TMS group with 31% screening failure rate, we need approximately 70 FHD subjects. The 70 healthy volunteers will allow us to do a better statistical power analysis of clinical and fMRI outcomes measures to evaluate effect size for TMS As a result, we would like to increase our overall goal enrollment target to 140

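### A 31% screening failure rate gives about 29 recruits for 20 TMS patients, so it does not support the stated target of about 70 FHD subjects

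*Combined protocol and SAP*

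**What the plan says.** Under Data Analysis & Statistical Considerations, Sample Size justification, the combined protocol and SAP fixes the size of the TMS cohort: "I propose to study 20 patients in TMS group using writing task and fMRI as outcome measures". It then derives the number of FHD subjects from that cohort and one loss rate: "in order to reach pilot data set of 20 patients in TMS group with 31% screening failure rate, we need approximately 70 FHD subjects". For the healthy volunteers, also 70, the next sentence gives a separate reason, a better power analysis of the clinical and fMRI outcomes. The two groups together lead to the overall goal: "we would like to increase our overall goal enrollment target to 140".

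Other sections give the flow between visits. Under Design & Procedures, the visit 2 count equals the visit 1 count: "70 FHD subjects and 70 HV from visit 1 will be recruited to undergo a functional MRI brain at Duke BIAC". Purpose of the Study repeats it. For visits 3 to 5 the plan is "20 focal hand dystonia subjects who completed visits 1 and 2 will also be recruited to undergo TMS stimulation at Duke BSRC". Later visits are optional: "Subjects can opt in or out of visits 2, and 3-5 of the research study". No opt-out rate is given. The exclusion criteria for visits 2 to 5 add MRI contraindications and the TMS safety screen to those that apply at visit 1.

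**The concern.** The FHD target is presented as the result of inflating 20 patients for 31% loss. A loss of under a third cannot turn 20 into 70 in one step, so either a number is wrong or a step is missing. This sentence is the only reason the sample size section gives for the FHD number.

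What is at stake is whether recruitment is planned on the right footing. If 31% is the whole loss, the TMS cohort needs about 41 fewer FHD recruits (70 - 29) than planned, and each recruit is also planned for an MRI session of about 1.5 hours. If the real loss is nearer 70%, reaching 20 TMS patients is much harder than a 31% rate suggests. Depending on where that loss falls, the planned 70 FHD subjects at visit 2 may also be out of reach. A reader cannot tell which situation applies.

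**Working it through.** **Inputs.** From Sample Size justification: TMS cohort n = 20, screening failure rate d = 0.31, stated FHD recruitment about 70. From Design & Procedures: 70 FHD subjects at visit 1, 70 at visit 2, 20 at visits 3 to 5. Opt-out from visit 2 and from visits 3 to 5 is allowed, with no rate.

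**Attempt to reproduce 70.** The standard inflation is n/(1 - d):

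- 20/(1 - 0.31) = 20/0.69 = 28.99, so 29.

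This is not about 70. Other readings, rounded up:

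| Reading | Calculation | Result |
|---|---|---|
| Simple mark-up, n(1 + d) | 20 × 1.31 | 27 |
| 31% lost at each of two stages | 20/0.69² | 43 |
| 31% lost at each of three stages | 20/0.69³ | 61 |
| 31% lost at each of four stages | 20/0.69⁴ | 89 |
| Base of 25 (20 FHD + 5 healthy volunteers) | 25/0.69 | 37 |
| Base of 60 (the power-analysis figure in the same section) | 60/0.69 | 87 |
| Base of 60, simple mark-up | 60 × 1.31 | 79 |
| 31% as the share that passes | 20/0.31 | 65 |

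None lands on 70 within 3% or 2 patients (about 68 to 72). The pass-rate reading is the nearest single step, but it gives 65 and contradicts the plan's own description of the 31% as a failure rate.

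**Working backwards from 70.**

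- Eligible after 31% failure: 70 × 0.69 = 48.3, about 48.
- Overall loss implied by 70 to 20: 1 - 20/70 = 0.714, about 71%.
- Further loss needed among those who pass screening: 1 - 20/48.3 = 0.586, about 59%.

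Neither the 71% nor the 59% appears in the documents.

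**Could 70 be a safety margin?** If each recruit passes independently with probability 0.69, 29 recruits give a 59% chance of at least 20 eligible, and 35 recruits give 95%. A margin for chance variation therefore explains a target in the mid-thirties, not 70.

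**Could 70 be justified another way?** A comparison of 70 FHD with 70 healthy volunteers, two-sided at 0.05 with 80% power, detects a standardised difference of about 0.48 SD. That could be a sound reason for 70 FHD subjects at visit 1, but the sample size section does not offer it for the FHD number.

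**The case against.** The arithmetic is not open to dispute, but its consequences can easily be overstated. Five points deserve weight.

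- **Which number is wrong.** A reader might infer that the target is 2.4 times too large (70/29), or else that the true loss is near 70% and the 31% is an error. The documents do not force that choice. The 31% may be screening failure alone, with the rest of the loss coming from subjects who decline visit 2 or the three weekly TMS visits. Both 31% and 70 could then be right, and the sentence would merely omit a factor. This point stands, although the 59% further loss that it needs is not stated.
- **A pass rate misnamed.** It is tempting to conclude that 31% is the share that gets through. That gives 65 rather than 70 and goes against the plan's wording, so it remains a guess.
- **The effect on visit 2.** A reader might infer that only 48 per group will reach fMRI. The rate is given for FHD subjects reaching the TMS cohort. Nothing applies it to healthy volunteers, and nothing places all the loss before visit 2. In-person screening takes place at visit 1, and the visit 2 count can be read as a ceiling. What stands is narrower: equal counts at visits 1 and 2 leave no room for the added exclusions or for opt-out.
- **The total of 140.** Only the FHD half depends on the 31% sentence, because the healthy volunteers have their own reason.
- **The counts are provisional.** Analysis and Statistics says that visit 1 data will be used to redo the power analysis and adjust cohort sizes. This softens the consequences but does not supply the missing step.

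**Conclusion.** The concern holds in a limited form. The stated 31% failure rate supports about 29 FHD recruits for a TMS cohort of 20, not about 70, and 70 recruits at that rate would leave about 48 eligible. The gap is a factor of 2.4, or an unstated further loss of about 59% after screening. This rests on reading the 31% as the plan words it, a failure rate applied once to recruited FHD subjects.

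It does not follow that 29 is the right enrolment for the study. The 70 FHD subjects also serve the baseline comparison with healthy volunteers, which may justify the number on other grounds. The documents show only that the reason given does not lead to the number given.

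This should be fixed, but it is not critical. The TMS cohort stays at 20 under every reading, and no endpoint, analysis or stimulation procedure depends on the answer.

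**What to change.** Correct the sentence by one of two routes.

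1. **Repair the derivation.** From the screening log, say what the 31% counts. State the expected FHD loss at each step: screening at visit 1, eligibility and opt-in for visit 2, eligibility and opt-in for visits 3 to 5. Then recompute the FHD number as 20 divided by the product of the proportions retained.
2. **Change the reason.** If 31% is the whole expected loss, say that about 29 FHD recruits suffice for the TMS cohort. Justify 70 by the visit 1 comparison with 70 healthy volunteers, which detects about 0.48 SD at 80% power, two-sided 0.05.

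Under either route, make the expected number of FHD subjects at visit 2 consistent with the stated losses, both in Purpose of the Study and in Design & Procedures. Base any statement about fMRI precision on that number. The 0.48 SD figure applies to visit 2 only if 70 per group are actually scanned.

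The cost is one rewritten sentence, a check of the screening log and a matching visit 2 count in two places. No study procedure changes.

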Visit 3, 4 and 5: 5 HV who completed visits 1 and 2 will be recruited to undergo development of TMS stimulation protocol at Duke BSRC. TMS Stimulation will be provided up to 20 minutes (at 10Hz) with a writing sample during stimulation. Subjects will also perform a writing assessment before and after each stimulation block. An fMRI will be performed after completion of each TMS stimulation session.

20 focal hand dystonia subjects who completed visits 1 and 2 will also be recruited to undergo 3 visits of TMS stimulation at Duke Brain Stimulation Center. The 3 visits will each be 1 week apart. 2 visits will involve active TMS and 1 visit will be sham TMS. During one of the active TMS visits, TMS coil will be applied to the premotor cortex for brain stimulation while during the other active TMS visit, TMS coil will be applied to the primary sensory cortex. TMS stimulation protocol will consist of 10Hz stimulation for up to 20 minutes with a writing task during the stimulation block. Subjects will undergo a writing assessment before and after each stimulation block and complete TMS side effects survey. Writing task is different from writing assessment in that writing task will only be used as part of the investigational therapy while writing assessment will be data collected for outcomes measures. fMRI will be performed after completion of each of the 3 TMS visits.

Background & Significance

- Should support the scientific aims of the research

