 3. Healthy volunteers will undergo TMS stimulation protocol development. Subjects will receive 10Hz active stimulation at premotor cortex during one visit and primary sensory cortex during another visit for up to 20 minutes with stimulation intensity up to 120% of resting motor threshold which is within the published safety guidelines (47) and based on previously published protocol used in multiple human studies(13–16). The resting motor threshold is a baseline stimulation intensity determined using the protocol in step 2. Additional stimulation parameters including duration of continuous stimulation, interstimulus interval, stimulation intensity, orientation of magnetic coil, biphasic or monophasic stimulation will be developed with healthy volunteers based on the published safety guidelines(47), writing assessment (includes writing and non-writing sampling) and feasibility within 20 minutes stimulation paradigm.
 4. WC subjects will undergo TMS stimulation visits 3, 4 and 5. 2 visits will include active TMS stimulation while the remaining one visit will be a control sham stimulation. Of the 2 active TMS stimulation visits, subjects will receive TMS at premotor cortex during one visit and at primary sensory cortex during the other active TMS visit. The dosage of active stimulation will be 10Hz for up to 20 minutes with resting motor threshold up to 120% which is within the published safety guidelines (47) and based on previously published protocol used in multiple human studies(13–16). During both active and sham stimulation blocks, subjects will be asked to perform a writing task of writing a diverse paragraph as an online stimulation task. The stimulation block will be preceded and followed by a writing assessment and TMS acute side effects survey to assess safety of the stimulation. Visit 3, 4, and 5 will occur 1 week apart. Subject will undergo fMRI after each of the 3 TMS visits.

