Our preliminary analysis of the Duke patient population reveals sufficient population of FHD subjects to recruit for our study at Duke University. Our electronic patient database identifies 186 Duke patients with a specific diagnosis of organic writer's cramp (ICD 9 code 333.84). Because ICD 10 code does not have a specific writer's cramp diagnosis, we suspect that more cases are included within the ICD G24.9 (focal dystonia) group. Therefore, the primary care providers for all 837 subjects with either of these codes may be contacted by research coordinator for patient candidacy for this research study as detailed in Section 6 eIRB submission form.

Analysis and Statistics: [name] in the Department of Neurology, **[name] and [name] in the BERD core of the Statistics Department** will be **involved** the de-identified data **analysis** but will be not involved in collecting the data. Visit 1 data of handwriting metric differences between healthy participants and focal hand dystonia patients will establish writing metric sensitivity at our site and recalculate power analysis to adjust cohort sizes, or improve technique, as indicated for visits 2, 3, and 4. For Visit **3 -5**, a two-way ANOVA will be performed with groups (healthy vs dystonia) and stimulation type (task during vs after stimulation) as the main factor within subjects. A two-way repeated measures ANOVA will be conducted with stimulation type (task during vs after stimulation) and treatment type (sham vs active) as the main factors between subjects for each handwriting measure.

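### The visit 3-5 healthy-versus-dystonia ANOVA sets 5 volunteers, stimulated during parameter development, against 20 patients recruited afterwards, so disease group cannot be separated from stimulation parameters and stage.

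*Combined protocol and SAP*

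**What the plan says.** Under Data Analysis & Statistical Considerations, the Analysis and Statistics paragraph plans two models for visits 3-5. The first is introduced with "a two-way ANOVA will be performed with groups (healthy vs dystonia", and its factors are given in full as "groups (healthy vs dystonia) and stimulation type (task during vs after stimulation) as the main factor within subjects". The second has "stimulation type (task during vs after stimulation) and treatment type (sham vs active) as the main factors between subjects". So sham versus active appears only in the model without a group factor. Neither model contains the stimulation parameter set or the cortical site, and the paragraph does not say which sessions enter either one.

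The make-up of the two groups is given elsewhere:

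- Purpose of the Study: "5 HV who completed visits 1 and 2 will be recruited to undergo development of TMS stimulation protocol".
- Design & Procedures, step 3: volunteers receive active stimulation at premotor cortex on one visit and at primary sensory cortex on another. The list of settings still open (length of continuous stimulation, interval, intensity, coil orientation, pulse form) ends with "biphasic or monophasic stimulation will be developed with healthy volunteers". Writing assessment is one of the stated bases for settling them.
- Design & Procedures, Visits 3, 4 and 5: "Following protocol development, 20 focal hand dystonia subjects who completed visits 1 and 2 will also be recruited".
- Design & Procedures, step 4: each patient has two active visits and one sham visit.

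**The concern.** A healthy-versus-dystonia test on data taken during or after stimulation is about disease only if both groups were stimulated alike. Here the volunteers are the cohort on which the stimulation is tuned, and the patients come later and receive the result. A group difference could reflect different settings or a different stage of the study. A real disease difference could also be masked by them. One basis for the tuning, the writing assessment, overlaps the handwriting outcomes that the ANOVA compares.

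The risk is a published statement about how dystonia changes the response to TMS when the data cannot tell that explanation from a change in the stimulation itself.

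**Working it through.** **Plan's own figure.** None is stated for this comparison. The only power statement (60 in TMS for an effect size of 30% at alpha 0.05) gives no SD, power, sidedness or design. It cannot be reproduced and does not bear on 5 against 20.

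**Inputs.** 5 volunteers and 20 patients (Purpose of the Study; Design & Procedures). Volunteer sessions as described: premotor active and sensory active. Patient sessions: premotor active, sensory active and sham. Alpha is 0.05, as in the sample size paragraph. Two-sided testing and 80% power are assumptions.

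**1. Can group be separated from parameter stage?** The described sessions number 5 × 2 + 20 × 3 = 70. Give each an intercept and indicators for dystonia, final-parameter stage, active and sensory site. If no volunteer session used the final parameters, the dystonia and final-parameter columns are identical, and the 70 × 5 design matrix has rank 4. Covariate adjustment then cannot separate the two effects. If some volunteer sessions did use the final parameters, the columns differ, and separation rests on those sessions alone. The plan neither requires nor excludes this.

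**2. What if all described sessions are pooled?** Volunteer sessions are active in 10/10 = 100%, patient sessions in 40/60 = 67%. With an active-versus-sham effect of δ and no disease effect, the pooled healthy-minus-dystonia contrast shifts by δ × (1 − 2/3) = δ/3. This arises only if patients' sham sessions are included and volunteers have no sham. The plan settles neither.

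**3. Precision of the between-subject comparison.** Standard error = SD × √(1/5 + 1/20) = SD × √0.25 = 0.5 SD, equivalent to 2/(1/5 + 1/20) = 8 per group. The normal approximation to the difference detectable with 80% power is (1.96 + 0.84) × 0.5 = 1.40 SD. The noncentral t on 23 degrees of freedom gives 1.46 SD. Power from the noncentral t:

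| True difference (SD) | Power, 5 vs 20 |
|---|---|
| 0.3 | 9% |
| 0.5 | 16% |
| 0.8 | 34% |
| 1.0 | 48% |
| 1.2 | 63% |

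**4. False attribution to disease.** Suppose disease has no effect but the difference in parameters shifts the outcome by b. The test is then significant in 8% (b = 0.25 SD), 16% (0.5), 30% (0.75) or 48% (1.0) of trials, against a nominal 5%. These values of b are assumed; the documents give no basis for choosing one.

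**5. Interaction with during/after.** For a change score, 1.46 SD of the change equals 1.46 × √(2(1 − ρ)) raw SD: 1.46 at ρ = 0.5 and about 0.92 at ρ = 0.8 (ρ assumed). The 1.46 figure therefore does not carry over to the interaction.

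**6. Where the group comparison is free of this problem.** Visits 1 and 2 come before any stimulation, with 70 planned per group. The same calculation gives about 0.48 SD at 80% power.

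**The case against.** The strongest reply is that the two groups share a good deal: 10 Hz, the same ceilings on duration and intensity, the same two cortical targets, and the same coil and navigation system. Design & Procedures also says that "All 25 subjects will undergo the procedure as detailed below". If early volunteer sessions settled the parameters and later ones used them, the parameter difference could be small or nil. Visits 3-5 are framed as safety and feasibility, the data set is called pilot, cohort sizes may be revised after visit 1, and no decision is tied to this ANOVA.

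Much of this stands, and it limits what can be said. Four stronger readings are tempting but not supported:

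- *Volunteers have no sham.* This is only silence. They are listed for visits 3, 4 and 5, two active visits are described, and the third is unspecified.
- *The analysis fails because group by sham cannot be estimated.* Neither planned model contains that term. Sham matters to the group ANOVA only through which sessions enter.
- *The confounding is complete and the result cannot be interpreted at all.* That assumes no volunteer ever received the final parameters, which the documents do not say.
- *The trial can detect nothing below 1.46 SD.* That figure applies only to a between-subject comparison of a single measure.

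The defence does not show that the groups were stimulated alike. The common procedure splits into a volunteer step and a patient step, and only the patient step describes sham. Shared ceilings are not shared settings, and step 3 exists because those settings are open. Pilot status lowers the stakes and favours description over a test. The plan itself, in the data management principles under Data & Safety Monitoring, asks that the statistical approach be appropriate and settled in advance.

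**Conclusion.** The concern holds in limited form. As written, the group effect at visits 3-5 mixes disease with stimulation parameters and study stage, with no model term to separate them. They become separable only if some volunteers received the final parameters, which the plan does not require. The size of any bias is unknown and could be nil. For illustration, an assumed 0.5 SD shift from parameters alone would raise false positives from 5% to 16%.

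Leaving sessions unspecified adds a possible imbalance of δ/3 if patients' sham sessions are pooled with volunteers' active ones. For a single between-subject measure, 5 against 20 has 80% power only for about 1.46 SD (two-sided 5%, no dropout), so a null result would say little either. The problem affects data taken during and after stimulation, not assessments made before any stimulation. It should be corrected before analysis, but it does not threaten the sham/active comparison within patients.

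**What to change.** Replace the inferential visit 3-5 group ANOVA with a descriptive report of the 5 volunteers: parameters used at each session, tolerability, and writing before and after stimulation.

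If a group contrast is kept, label it exploratory, restrict it to active sessions given at the final parameters in both groups, and state which sessions enter and how many volunteers that leaves. Also state what the volunteers' third visit contains.

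Keep formal healthy-versus-dystonia inference at visits 1 and 2. Keep inference on TMS effects in the sham/active comparison in the 20 patients, fitted as a within-patient factor. The plan labels it between-subject although every patient has both conditions.

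The cost is one sentence rewritten and one descriptive table, with no change to recruitment, visits or procedures. The downside is that a nominal group test is lost or downgraded.

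### Both visit 3-5 ANOVAs mislabel their factors: healthy vs dystonia is listed within subjects, and sham vs active between subjects, contrary to the design

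*Combined protocol and SAP*

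**What the plan says.** The models are in Data Analysis & Statistical Considerations, paragraph Analysis and Statistics. Two are planned for visits 3-5.

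- **First ANOVA.** A two-way ANOVA with "groups (healthy vs dystonia) and stimulation type (task during vs after stimulation) as the main factor within subjects".
- **Second ANOVA.** "A two-way repeated measures ANOVA will be conducted with stimulation type" (during vs after stimulation) and "treatment type (sham vs active) as the main factors between subjects for each handwriting measure".

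The design is in Purpose of the Study and in Design & Procedures, under visits 3, 4 and 5.

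- **Healthy volunteers:** "5 healthy volunteers who completed visits 1 and 2 will be recruited to undergo development of TMS stimulation protocol". The 20 focal hand dystonia patients are recruited separately.
- **Treatment in patients:** "2 visits will involve active TMS and 1 visit will be sham TMS", restated in step 4 of the procedures as "2 visits will include active TMS stimulation while the remaining one visit will be a control sham stimulation".
- **Measurements:** "During both active and sham stimulation blocks, subjects will be asked to perform a writing task", and "The stimulation block will be preceded and followed by a writing assessment".

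Nothing elsewhere in the document corrects the labels in the analysis paragraph.

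**The concern.** Whether a factor lies between or within subjects decides which variation its effect is judged against. A between-subject factor must be judged against variation between people, and a within-subject factor against variation within a person.

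Nobody is both healthy and dystonic, so group can only be between subjects. Every patient has sham and active visits, and writes both during and after stimulation, so treatment and stimulation type are both within subjects. The plan has group wrong in the first model and both factors wrong in the second.

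The two errors pull in opposite directions. Judging sham vs active against between-patient variation discards the gain from using each patient as his or her own control, and so loses power on the comparison that asks whether stimulation works. Judging group against an error that is too small produces too many false positives.

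**Working it through.** The plan gives no error term, degrees of freedom, power or within-subject correlation for these ANOVAs, so there is no planned figure to reproduce. The check has two parts.

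**1. Labels against design**

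| Model | Factor | Plan's label | Design |
|---|---|---|---|
| First | healthy vs dystonia | within | between (5 and 20 different people) |
| First | during vs after | within | within |
| Second | during vs after | between | within |
| Second | sham vs active | between | within |

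Three of the four labels conflict with the design.

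**2. Size of the effect if the labels are followed**

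*Inputs from the document:* 5 volunteers, 20 patients, two levels of stimulation type, alpha 0.05 (from the sample size paragraph).

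*Assumptions:* two-sided tests; equal variances; the same correlation rho between any two measures on one person, with rho = 0.5, 0.7 and 0.8; a true sham-active difference of 0.5 SD; sham compared with a single active condition.

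*Second ANOVA, 20 patients x 2 treatments x 2 measures.* Let the SD be 1.

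- True variance of the treatment difference: (1 - rho)/20.
- Variance used with between-subject error (76 df): about 2/40 = 1/20.
- The variance used is therefore too large by a factor of 1/(1 - rho): 2, 3.3 and 5.
- Rough check at rho = 0.5: the test statistic has mean 0.5/sqrt(1/20) = 2.24 and SD sqrt(0.5) = 0.71. The critical value is sqrt(3.967) = 1.99. Power is about P(Z > (1.99 - 2.24)/0.71) = P(Z > -0.35), or 0.64.

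Simulation gives:

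| rho | Power, between-subject error (76 df) | Power, treatment-by-patient error (19 df) | Real alpha, between-subject error |
|---|---|---|---|
| 0.5 | 0.64 | 0.85 | 0.7-0.8% |
| 0.7 | 0.67 | 0.97 | 0.1% |
| 0.8 | 0.70 | 0.997 | about 0.01-0.02% |

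With the within-subject error, type I error is about 5% throughout. At rho = 0.3 the loss is smaller: power 0.62 against 0.72.

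*First ANOVA, 25 people x 2 measures.* The variance of a group mean is inflated by (1 + rho) relative to independent observations.

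- **Plain two-way ANOVA ignoring subject (46 df).** The error is close to the total variance of 1, so F is inflated by about 1.5, 1.7 and 1.8. The critical value 4.05 then acts like 4.05/1.5 = 2.70, 4.05/1.7 = 2.38 and 4.05/1.8 = 2.25. Simulation gives a type I error of about 11%, 13% and 14%.
- **Group tested on the within-subject residual (23 df).** F is inflated by (1 + rho)/(1 - rho) = 3, 5.67 and 9. The critical value 4.28 acts like 1.43, 0.76 and 0.48, so type I error is P(F(1,23) > those values) = 24%, 39% and 50%.
- **Group tested on between-subject error (23 df).** Type I error is about 5% at every rho.

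**The case against.** The strongest reply is that this is a wording error that would not survive contact with the data. Several parts of it stand.

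- **No error term is named.** A reader might infer that both tests will certainly use the wrong one. The document does not support that. The second model is called repeated measures, and an analyst who follows the name would use the correct within-patient error. The sentence is contradictory; it does not commit to the wrong test.
- **Only group is misplaced in the first model.** Stimulation type is correctly within subjects. The singular noun also leaves room for a reading in which only stimulation type was meant as within, though the plain reading covers both.
- **The largest false-positive figures are an upper scenario.** Since nobody belongs to both groups, group cannot be fitted as a true within-subject factor. The likelier failure is a plain two-way ANOVA that ignores subject, which gives 11-14%, not 24-50%.
- **Power need not collapse.** A calculation with one measure per condition, which holds paired power at 80%, shows between-subject power falling to about 10% at rho = 0.8. But holding paired power fixed shrinks the assumed effect from 0.66 to 0.42 SD as rho rises from 0.5 to 0.8, and the layout is not the planned two-factor one.
- **Visits 3-5 are a pilot.** Their stated purpose is safety and feasibility, statisticians are assigned, and the data management principles ask for tests to be settled in advance and clearly stated.

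The last point lowers the chance of a literal misapplication but does not repair the text. Two analysts could read the second sentence in opposite ways and obtain different results from the same data, which is what that principle is meant to prevent.

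**Conclusion.** Wrong as written. Group is declared within subjects when it is between; stimulation type and sham vs active are declared between subjects in the second model when both are within.

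The second ANOVA matters more, because it carries the sham-active comparison. Followed literally, it is too conservative and lowers power by about 0.2 to 0.3 under the assumptions above. The group test in the first ANOVA is anti-conservative, at two to three times the nominal 5% in the likely form of the error.

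These sizes rest on an assumed correlation, a 0.5 SD effect and a simple equal-correlation structure, none of which the documents supply. The mislabelling itself rests on no assumption. What cannot be concluded is that the eventual analysis will be wrong: the plan leaves that open, and that is the defect.

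**What to change.** Reword the two sentences in Analysis and Statistics.

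- **First ANOVA:** group (healthy vs dystonia) between subjects and stimulation type (during vs after) within subjects, as a mixed-design ANOVA or a mixed model with a random subject effect.
- **Second ANOVA:** stimulation type and treatment type both within subjects, as a repeated-measures ANOVA or an equivalent mixed model with a random patient effect. State that treatment is tested against within-patient variation.

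Keep both planned comparisons and the during/after factor. Collapsing everything into one model in the 20 patients is not needed to cure this error, and would drop the healthy vs dystonia comparison.

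The cost is a few lines of text. No new data, visits or patients are required.
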